3.0 SPECIFIC AIMS

3.1. To prospectively determine the following outcomes in Medicare beneficiaries who undergo HCT for MDS and related disorders and compare these outcomes with those of non-Medicare beneficiaries, aged 55-64:

- Early (100-day) mortality
- Acute and chronic graft-versus-host disease (GVHD)
- Relapse and progression
- Disease-free survival
- Progression-free survival
- Overall survival

3.2. To prospectively determine whether there are disease- or patient-related factors that predict outcomes of HCT for MDS and related disorders in Medicare beneficiaries, including:

- World Health Organization (WHO) classification
- International Prognostic Scoring System (IPSS) score
- WHO-based Prognostic Scoring System (WPSS)
- Cytopenias
- Cytogenetics
- Primary versus secondary MDS
- Disease duration and prior therapy
- Recipient age
- Performance score
- Sorrow co-morbidity index

3.3. To prospectively evaluate what transplant characteristics are associated with outcomes of HCT for MDS and related disorders in Medicare beneficiaries, including:

- Preparative regimen
- Graft source
- GVHD prophylaxis
- Use of hematopoietic growth factors

3.4. To prospectively evaluate treatment facility characteristics associated with outcomes of HCT for MDS and related disorders in Medicare beneficiaries, including:

- Transplant volume
- Years of operation
- Academic affiliation

This study is Part 1 of a comprehensive evaluation of HCT in Medicare beneficiaries. It will evaluate outcome of allogeneic HCT, with monitoring to ensure that there is not undue early mortality in adults ≥ 65 years of age. The intent was to assemble a high quality data set of 240 patients, whose data will be analyzed to provide information pertinent to design of Part II of the study. In addition it would prospectively evaluate the effect of various disease, patient and treatment facility characteristics related to outcome. The study protocol is amended October 30, 2012 to increase the accrual to provide sufficient power to evaluate the effect of these prognostic factors on outcomes of HCT.

4.0 BACKGROUND:

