The only available therapy with the potential to cure MDS is HCT and HCT is the treatment of choice for younger patients¹¹. Prior to the introduction of RIC regimens, regimen-related morbidity and mortality limited the utility of HCT in older patients and in those with significant co-morbidities. RIC regimens now allow HCT to be offered more safely to those patients but use of HCT in the older population still remains limited. This was evident in a recent study by the CIBMTR where only 10% of patients who underwent RIC HCT were older than 65 years. In that study, age had no significant impact on outcome in multivariate analysis in a cohort of patients between 40 and 70 years.¹² The 100 day mortality rate was about 20% and the 2 year probability of survival was about 40%.

There are multiple reasons that older patients do not undergo transplantation. Older patients may have co-morbidities that compromise their ability to tolerate an intensive therapy like HCT. Some oncologists are reluctant to refer older patients for HCT, even if there are no clinical contraindications, because of perceived worse outcomes in older patients. Some transplant centers have arbitrary upper age limits for HCT candidates. Finally, some third party payers will not cover HCT in older patients until there is transformation to acute leukemia. Until recently, coverage of HCT for MDS by the US Centers for Medicare and Medicaid Services (CMS) depended on local coverage determinations¹³. CMS is the primary health insurer for most US adults 65 years of age or older. Recently, CMS made a National Coverage Determination (NCD) regarding MDS, indicating that data regarding efficacy in a CMS beneficiary population were currently insufficient but that coverage would be provided for patients enrolled in a clinical study appropriately designed to generate data necessary to make a determination about efficacy and effectiveness. This decision acknowledged that “the available evidence suggests that allogeneic HSCT for MDS is reasonable and necessary under §1862(a) (1) (E) of the Social Security Act through Coverage with Evidence Development (CED).”

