6.2. Secondary outcomes

6.2.1. Acute GVHD: Occurrence of grade II, III and/or IV skin, gastrointestinal or liver abnormalities fulfilling the IBMTR criteria for acute GVHD.

6.2.2. Chronic GVHD: Occurrence of symptoms in any organ system fulfilling the criteria of chronic GVHD.

6.2.3. Relapse: disease recurrence or persistent disease for patients not in CR at transplant. Those who survive without recurrence or persistent disease are censored at the date of last contact.

6.2.4. Progression: increase in marrow blasts to $> 20\%$; patients without progression are censored at time of most recent marrow examination.

6.2.5. Disease-free survival: survival without death or relapse. Those who survive without recurrent or persistent disease are censored at the date of last

contact.

6.2.6. Progression-free survival: survival without increase in marrow blasts to >20%; patients without progression are censored at time of most recent marrow examination.

6.2.7. Overall survival: Surviving patients are censored at the date of last contact.

7.0 DATA COLLECTION:

All data necessary for this study will be collected using the existing mechanisms of the CIBMTR under, operating under the “NMDP and CIBMTR Protocol for a Research Database for Hematopoietic Stem cell Transplantation and marrow Toxic Injuries”, version 6.0, (NCT01166009) (Appendix A). The Informed Consent for this protocol is also found in Appendix A. These data collection mechanisms support the reporting required for the Stem Cell Therapeutic Outcomes Database (SCTOD), and the research endeavors of the CIBMTR. Existing data instruments and procedure manuals can be found at www.cibmtr.org/DataManagement. Registration of patients and submission of data will follow standard CIBMTR procedures.

8.0 STUDY DESIGN:

This study initially had a target accrual of 240 patients older than age 65 for the 100 day mortality primary endpoint. Sample sizes were based on an inferiority test of the hypothesis that the 100 day mortality rate in the ≥ 65 year old cohort is higher than 20%, the approximate 100-day mortality rate in a 55-64 year old cohort¹². The study was designed to have approximately 80% power to detect a 6.5 % or greater increase in 100 day mortality rate in the ≥ 65 year old cohort. Table 1 below shows the power of the test for various 100 day mortality rates.

Table 1.	
True 100 day mortality rates	Power
0.21	10%
0.22	20%
0.23	32%
0.24	46%
0.25	60%
0.26	73%
0.27	83%
0.28	90%
0.29	94%

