At each of the four evaluations points, we will prepare descriptive tables of the covariates. Kaplan-Meier estimates of mortality and disease free survival will be

constructed for the entire cohort and by sub-groups defined by the fixed covariates such as IPSS score. Cumulative incidence curves will be constructed to estimate acute GVHD incidence, relapse progression rates. These analyses will be conducted when 60, 120, 180 or 240 patients have at least 100 days of potential follow-up. As they are descriptive in nature, no p-values are computed until the entire cohort has been observed.

When accrual of the first 240 patients is complete and all patients have been followed for at least 100 days, the association between outcomes and the variables listed in Section 3.0 will be examined in either a logistic regression model or a Cox proportional hazards model depending on the outcome of interest. Forward stepwise model selection techniques will be used in this approach. These analyses will include a cohort of patients ages 55-64 years transplanted for MDS and related disorders in the same centers as the CMS beneficiaries included in this analysis.

After accrual is complete, follow-up of this cohort will continue, through standard CIBMTR mechanisms, after completion of these analyses. Evaluation of all secondary endpoints will be repeated when all patients have been followed for a minimum of two years.

Prognostic factors in patients age 65 and older

Another objective of this study is to determine the prognostic value of patient and disease factors upon outcomes of HCT in patients age 65 and older. After evaluating the demographics of the first 180 patients age ≥ 65 accrued to the protocol, several prognostic factors of interest (sections 3.2 and 3.3) are expected to require larger numbers of patients to achieve adequate power to detect meaningful differences in outcomes for patients in this cohort.

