8.1. Variables to be analyzed for their association with primary and secondary outcomes

8.1.1. Patient related:

- Age: in five year increments (or appropriate cutpoint based on data analysis)
- Gender: male vs. female
- Race: Caucasian vs non-Caucasian
- Karnofsky performance status: <80% vs. ≥80%
- Sorror co-morbidity Index

8.1.2. Disease related:

- WHO Disease classification at diagnosis and just prior to HCT
- FAB classification
- Pretransplant WBC and untransfused platelet count and hemoglobin concentration
- IPSS score immediately prior to transplantation
- WPSS score immediately prior to transplantation
- Cytogenetics
- Primary versus secondary MDS
- Time from diagnosis to transplant: <1 year vs. ≥ 1 year (or more appropriate cutpoint based on data analysis)
- Agents used for prior therapy

8.1.3. Transplant related:

- Conditioning regimen: more versus less intensive; specific regimens to be evaluated if numbers of patients sufficient
- Donor age
- Donor-recipient CMV status: -/- vs. -/+ vs. +/- vs. +/+
- Donor-recipient HLA match: HLA matched sibling vs. 8/8 locus (HLA- A, B, C, DRB1) matched unrelated donor vs. 7/8 locus matched unrelated donor
- Stem cell source: bone marrow vs. peripheral blood
- GVHD prophylaxis: Cyclosporine or Tacrolimus + Methotrexate vs. ex vivo T- cell depletion vs. other
- Donor-recipient gender match: male-male vs. male-female vs. female-male vs. female-female
- Transplant center characteristics: transplant volume, years of operation, academic affiliation

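### The 55-64 comparators come from the same centers as the older patients, but the stated model has no center term, so center differences can bias the age contrast

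*Protocol*

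**What the plan says.** The hypothesis (Section 2.0) and aim 3.1 both rest on a comparison of older patients with adults aged 55-64.

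For that comparison, Section 8.0 uses a younger cohort "transplanted for MDS and related disorders in the same centers as the CMS beneficiaries included in this analysis". It states no matching, stratum or ratio by center.

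On the model, the same section says that "the association between outcomes and the variables listed in Section 3.0 will be examined in either a logistic regression model", or a Cox model for the other outcomes, and adds: "Forward stepwise model selection techniques will be used in this approach". No variable is named as forced in.

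Center enters only through three traits. Aim 3.4 is "To prospectively evaluate treatment facility characteristics associated with outcomes of HCT for MDS and related disorders in Medicare beneficiaries", and Section 8.1.3 lists among the covariates "Transplant center characteristics: transplant volume, years of operation, academic affiliation".

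The sizing is a separate matter. Section 8.0 describes "an inferiority test of the hypothesis that the 100 day mortality rate in the ≥ 65 year old cohort is higher than 20" percent, with 240 older patients.

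**The concern.** Restricting comparators to the same centers removes centers that contribute no one to the older cohort. It does not make the ratio of older to younger patients equal across the centers that remain. A pooled model with no center term compares all older patients with all younger ones. Part of that comparison is therefore between centers with a high share of older patients and centers with a low share.

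The documents make variation by center plausible without showing it. Section 5.0 leaves eligibility for transplant to local practice. Section 4.0 notes that "Some transplant centers have arbitrary upper age limits for HCT candidates". Aim 3.4 exists because outcomes may differ by facility.

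The stake is the study's main claim. If centers that transplant more older patients have lower mortality, the pooled contrast makes the age groups look more alike than they are within a center, which favors the stated hypothesis of similarity. If those centers have higher mortality, older patients look worse than they are. The same-center sampling supplies within-center information that the stated model does not use.

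**Working it through.** **1. The plan's own figure.** Table 1 reproduces as a one-sample test: null rate p0 = 0.20, n = 240, one-sided alpha 0.05. Alpha is not stated; it is inferred because it fits.

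Power = Φ{[(p − p0) − 1.645·√(p0(1 − p0)/n)] / √(p(1 − p)/n)}

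At p = 0.25: (0.05 − 1.645 × 0.02582)/0.02795 = 0.269, giving 60.6% (stated: 60%).

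| True rate | 0.21 | 0.22 | 0.23 | 0.24 | 0.25 | 0.26 | 0.27 | 0.28 | 0.29 |
|---|---|---|---|---|---|---|---|---|---|
| Stated (%) | 10 | 20 | 32 | 46 | 60 | 73 | 83 | 90 | 94 |
| Recomputed (%) | 10.8 | 20.0 | 32.3 | 46.4 | 60.6 | 73.2 | 83.2 | 90.2 | 94.8 |

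At 0.265 the result is 78.5%, against a stated figure of about 80%. This test compares the older cohort with a fixed 20% and does not use the younger patients. The point made here does not touch it.

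**2. Bias of the pooled contrast.** The documents give no between-center variance, no number of centers and no age mix by center, so every input in this step is assumed except the 20% base rate (Section 8.0). Suppose there is no age effect within any center. Let s be the average share of older patients, SD(share) its spread across centers, SD(u) the spread of center effects on the logit scale, and r the correlation between share and center effect.

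Bias (logit) = r × SD(u) × SD(share) / [s(1 − s)]

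Bias (points) = bias (logit) × p(1 − p) × 100, with p = 0.20, so the multiplier is 16.

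With s = 0.40, s(1 − s) = 0.24.

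| Case | r | SD(u) | SD(share) | Bias (points) |
|---|---|---|---|---|
| One source of variation absent | 0, or any | 0, or any | 0, or any | 0 |
| Low | 0.2 | 0.3 | 0.10 | 0.006/0.24 × 16 = 0.4 |
| Middle | 0.4 | 0.4 | 0.125 | 0.020/0.24 × 16 = 1.3 |
| Extreme | 0.6 | 0.5 | 0.15 | 0.045/0.24 × 16 = 3.0 |

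The first row applies when r, SD(u) or SD(share) is zero. A negative r gives the same sizes with the opposite sign.

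**3. Second illustration.** Assume two types of center, with half of the younger patients in the lower-mortality type. If mortality is 18% and 22% and 60% of older patients are in the lower type, the bias is (0.6 − 0.5) × (18 − 22) = −0.4 points. If mortality is 15% and 25% and 80% of older patients are in the lower type, it is (0.8 − 0.5) × (15 − 25) = −3.0 points.

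**4. Scale against sampling error.** With 240 older patients and an assumed 360 younger ones (a 40% share), the standard error of the difference at 20% mortality is √(0.16/240 + 0.16/360) = 0.033, or 3.3 points. The mid-range bias is under half of that; the extreme is close to it.

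**5. What a within-center contrast costs.** In a simulation of an assumed 600 patients in 40 to 80 centers, the within-center contrast removed the bias. Compared with the pooled model, the spread of the age log-odds ratio rose by about 0-13% with a term for the center's share of older patients, and by 2-17% with conditional logistic regression.

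**The case against.** The strongest reply is that this rests on silence. The protocol does not exclude a center stratum or random effect, and such detail is often left to a statistical analysis plan, which is not at hand. A reader might infer that the protocol rules out a center-adjusted comparison. It does not. It does, however, fix the model family, the selection method and the center variables, and as written that leaves the contrast pooled.

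Second, the three facility traits cover the most obvious mechanism, center experience. This stands in part. They are candidates for adjustment, so what remains is unmeasured center differences and measured ones that selection drops. Stepwise selection enters a variable for its association with outcome, not because it confounds age.

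Third, the remark on upper age limits is thin evidence. It concerns some centers only, and a center whose limit excludes everyone aged 65 or over supplies no patient to the older cohort, so the same-center rule largely removes it. This stands. A reader might infer that the Background shows the age mix to vary among the centers that remain; it does not.

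Fourth, the pooled, covariate-adjusted contrast answers a legitimate question about the patients actually treated. That is fair, and it is a reason to keep the pooled result alongside the within-center one.

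Fifth, conditioning on center loses data and prevents estimation of the facility effects of aim 3.4 in the same model. Both are true, and the fix allows for them.

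**Conclusion.** The point holds as a possible bias that the stated model leaves open. Same-center sampling is not carried into the analysis, and center is represented only by three traits that stepwise selection may drop. Bias arises only if both the age mix and mortality vary by center, and it can go either way.

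Its size cannot be computed from the documents. The figures of 0, about 1.3 and 3.0 points rest wholly on the assumed shares, spreads and correlations above, and the last combines the extreme value of all three.

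Two stronger readings should be resisted. One is that center differences do distort the age effect: the documents show neither the age mix nor mortality by center. The other is that the bias could use up nearly half of the 6.5-point difference for which the study is sized: that difference belongs to the one-sample test against 20%, which this bias does not enter.

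**What to change.** For the age comparison of aim 3.1, state that age group is forced into the model and that center is accounted for:

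- **100-day mortality:** logistic regression with a random center intercept plus the center's share of 65+ patients, or conditional logistic regression by center as an alternative.
- **Other outcomes:** Cox models stratified by center, or with a center frailty. With a frailty, the share term should be added here too, because a random effect alone removes only part of the between-center component.
- **Sensitivity analysis:** the pooled model as now described.
- **Aim 3.4:** estimate the facility factors in a separate model without center strata.

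No new data are needed. The Research Database protocol in Appendix A (its Section 8) records that location of transplant is kept.

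The cost is a modest loss of precision, as in step 5 of the working. In stratified or conditional models, centers with only one age group or no deaths give no information. At 20% mortality a center with 4 patients has a 0.8⁴ = 41% chance of no deaths, and one with 7 patients 0.8⁷ = 21%. If many centers are small, that favors the random-intercept model with the share term.

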1.0 INTRODUCTION

Allogeneic hematopoietic stem cell transplantation (HCT) is the only potentially curative therapy available to patients with myelodysplastic syndromes (MDS). Until recently, however, concerns regarding morbidity and mortality of this intensive procedure limited its application in older patients with MDS. The introduction of reduced intensity conditioning (RIC) regimens greatly expanded the utility of HCT in older and sicker patients by reducing the risk of regimen-related toxicity^{1,2}. Although several small studies indicate safety and efficacy of HCT in older patients,^{3,4} there are no large prospective studies evaluating outcomes in patients older than 65 years. The aim of this study is to prospectively examine post-HCT outcomes in CMS beneficiaries with MDS to determine whether these outcomes are similar to those in younger patients where the experience with HCT is more extensive and where HCT is an accepted medical therapy.

2.0 HYPOTHESIS:

The outcome of HCT for MDS and related disorders in ≥ 65 years of age is similar to outcomes in adults 55-64 years of age.

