6.1. Primary outcome

6.1.1. 100 day mortality.

100 day mortality is chosen as the primary outcome because this is a preliminary study designed to provide data necessary to plan a prospective comparative study of transplant and non-transplant therapy. The rationale for use of HCT for MDS in patients ≥ 65 years old is that outcomes are thought to be similar to those in adults 55-64, where HCT is an accepted therapy, given similar non-age-based eligibility criteria are met¹¹. This study will determine, in a large cohort of patient ≥ 65 years old, whether early mortality is indeed in the range expected and will also provide information on prognostic factors for this outcome.

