Based on an 80% power with an assumption of a 25% 100 day mortality in the most favorable group and a delta as indicated, the number of patients needed for each of the analyses is listed below in Table 2. The anticipated accrual for Part I was based on power calculations for a primary outcome of 100 day survival after HCT in patients 55-64 compared to 65 and older. Based upon the distribution of age (65-69 vs. 70 and over), performance score, HCT Comorbidity index¹⁴, IPSS score, and disease status in the first 180 patients enrolled, we anticipate that 700 patients will be required to complete an analysis of prognostic factors for early outcome in patients 65 and older.

Table 2: Number of patients required to test differences in 100 day mortality with 80% power for specified prognostic factors

Prognostic Factor	Number of Patients based on expected difference		
	delta =0.1	delta =0.15	delta =0.2
Age			
<70	580	246	130
≥70	183	78	41
Total	763	324	171
HCT-CI (Sorrer, et al)			
0-2	294	118	59
≥3	222	89	45
Total	516	207	104
Secondary MDS			
No	649	265	133
Yes	163	67	34
Total	812	332	167
Cytogenetics			
Good/Intermediate	376	152	76
Poor	194	79	40
Estimated Unknown/missing/not done	78	32	16
Total	648	263	132
IPSS			
Low.int-1	311	125	62
Intermediate-2/high	214	87	43
Evaluable patients	525	202	105

The above sample size calculations for prognostic factors are based on the estimated frequencies of these potential risk factors using the data accrued in the first 180 patients and a binary response of alive or dead at 100 days. The final analysis of these factors will be performed in a logistic regression model for 100 day survival or a Cox regression model for other events in the cohort of patients age 65 and older.

The distribution of relevant prognostic factors shown in sections 3.2 and 3.3, and in the power calculations shown in Table 2 will be reviewed after accrual of 500 patients age 65 and over. Adjustments will be made to the final accrual projections at that time.

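### Table 2 does not follow from its stated assumption: 25% mortality in the most favorable group conflicts with about 20% overall, and the printed numbers come from 25% against 25% minus delta

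*Protocol*

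**What the plan says.** Section 2.0 of the protocol hypothesises that the outcome at 65 and over "is similar to outcomes in adults 55-64 years of age". Section 6.1.1 asks "whether early mortality is indeed in the range expected". In Section 8.0 the primary calculation tests "the hypothesis that the 100 day mortality rate in the ≥ 65 year old cohort is higher than 20" per cent, 20% being given as the approximate rate at ages 55-64. It has about 80% power for an increase of 6.5 points, that is, for 26.5%.

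The part of Section 8.0 on prognostic factors uses the same endpoint in the same age group. Its sizing takes 80% power, "an assumption of a 25% 100 day mortality in the most favorable group", and a stated delta. Table 2 is titled "Number of patients required to test differences in 100 day mortality with 80% power for specified prognostic factors" and gives group numbers for deltas of 0.10, 0.15 and 0.20. The split between groups is "based on the estimated frequencies of these potential risk factors using the data accrued in the first 180 patients". The text adds that "we anticipate that 700 patients will be required to complete an analysis of prognostic factors for early outcome in patients 65 and older". It gives no source for the 25%, no alpha or sidedness for Table 2, and no explicit rate for the second group.

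**The concern.** A cohort cannot have lower mortality than its best subgroup. A 25% rate in the most favorable group therefore puts the whole 65+ cohort above 25%, whereas the study hypothesis puts it near 20%. The two calculations in Section 8.0 share an endpoint and an age group but cannot both describe the same expected cohort.

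The next question is whether Table 2 was computed from the stated sentence. If it was not, its 80% power does not belong to the assumption printed above it. A reader then cannot tell which differences 700 patients can detect. Section 9.4 relies on the numbers being enough for the key factors.

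**Working it through.** **Inputs.** From Table 2, delta 0.10 column (favorable / unfavorable): age 580/183, HCT-CI 294/222, secondary MDS 649/163, cytogenetics 376/194 (plus 78 unknown, total 648), IPSS 311/214. The unfavorable share f is 0.240, 0.430, 0.201, 0.340 and 0.408. The ratio k is unfavorable over favorable. Power is 80%. Two-sided alpha of 5% is my assumption.

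**Formulas.** With favorable rate p1, other rate p2, δ = |p1 − p2| and p̄ = (p1 + k·p2)/(1 + k):

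- n1 = [1.96·√(p̄(1−p̄)(1+1/k)) + 0.8416·√(p1(1−p1) + p2(1−p2)/k)]² / δ²; total = n1(1 + k)
- with continuity correction: n1/4 · [1 + √(1 + 2(k+1)/(k·n1·δ))]²
- power = Φ[(δ − 1.96·s0)/s1], with s0 the pooled and s1 the unpooled standard error
- overall rate = p1 + f·(p2 − p1)

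**1. Reproducing Table 2.** HCT-CI at delta 0.10, k = 0.755:

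- 25% against 15%: p̄ = 0.207; n1 = (1.2106 + 0.5024)²/0.01 = 293. Printed: 294.
- 25% against 35%: p̄ = 0.293; n1 = (1.3600 + 0.5884)²/0.01 = 380. Not the printed figure.

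Favorable-group numbers for 25% against 25% minus delta, keeping the delta 0.10 ratio throughout:

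| Factor | Computed (0.10 / 0.15 / 0.20) | Printed |
|---|---|---|
| Age (continuity-corrected) | 580 / 246 / 130 | 580 / 246 / 130 |
| HCT-CI | 293 / 118 / 58 | 294 / 118 / 59 |
| Secondary MDS | 646 / 263 / 132 | 649 / 265 / 133 |
| Cytogenetics | 375 / 152 / 76 | 376 / 152 / 76 |
| IPSS | 311 / 125 / 62 | 311 / 125 / 62 |

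All 15 agree within 3 patients. A one-sided 5% test of 25% against 25% plus delta comes within 3% in the delta 0.10 column (age only with the correction). It fails at larger deltas: HCT-CI needs 139 against a printed 118 at 0.15, and 80 against 59 at 0.20. Putting 25% in the unfavorable group and 25% minus delta in the favorable one also fails: secondary MDS at delta 0.10 comes to 740 against a printed 812.

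**2. The stated assumption at delta 0.10 (25% against 35%).**

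| Factor | Implied overall rate | Power at printed number | Total for 80% | Printed evaluable total |
|---|---|---|---|---|
| Age | 27.4% | 74% | 881 | 763 |
| HCT-CI | 29.3% | 69% | 666 | 516 |
| Secondary MDS | 27.0% | 72% | 997 | 812 |
| Cytogenetics | 28.4% | 70% | 722 | 570 |
| IPSS | 29.1% | 70% | 675 | 525 |

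For age, for example, 0.25 + 0.240 × 0.10 = 0.274. Every implied rate exceeds the 26.5% of the primary test. The rates behind the printed numbers (25% against 15%) imply 20.7% to 23.0% overall.

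**3. Anchored at 20% overall.** Favorable rate = 0.20 − f·δ; unfavorable rate = favorable + δ. For age at delta 0.10 this is 17.6% against 27.6%. Evaluable totals for 80% power, without continuity correction (printed totals in brackets):

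| Factor | 0.10 | 0.15 | 0.20 |
|---|---|---|---|
| Age | 722 (763) | 326 (324) | 186 (171) |
| HCT-CI | 518 (516) | 230 (207) | 130 (104) |
| Secondary MDS | 826 (812) | 374 (332) | 214 (167) |
| Cytogenetics | 576 (570) | 258 (231) | 146 (116) |
| IPSS | 528 (525) | 236 (212) | 133 (105) |

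The bracketed figures are the sums of the printed group numbers. For IPSS at 0.15 the protocol prints 202, but 125 + 87 = 212.

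**4. Power at 700, delta 0.10, 20% overall.** Age 79%, HCT-CI 90%, secondary MDS 74%. If all 700 are evaluable, cytogenetics 87% and IPSS 90%. With the cytogenetics row's own unknown share (78/648 = 12%, so 616 evaluable), cytogenetics has 83%.

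**The case against.** A reader might infer that the sizing of 700 itself rests on contradictory event rates, that the amendment in effect plans on the hypothesis being false, and that the power claimed for 700 is wrong. The protocol does not support this.

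- The rates that reproduce Table 2 imply 20.7% to 23.0% overall at delta 0.10, below the 26.5% alternative. The 27.0% to 29.3% follows from the sentence, not from the numbers.
- No power is printed for 700. The 80% belongs to each row's own total, and Table 2 already shows age (763) and secondary MDS (812) above 700 at delta 0.10.
- 20% is the reference rate from ages 55-64, not a declared planning rate for the 65+ cohort. Table 1 considers true rates from 0.21 to 0.29. Planning on a higher rate is legitimate if it is stated, and for a fixed delta a lower true rate raises power.
- At delta 0.10, anchoring at 20% returns four of the five totals within about 2%. The age total is 5% lower than printed.
- Section 8.0 already plans a review of the factor distribution and the power calculations at 500 patients.

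All of this stands and limits the consequence. It does not rescue the text. The written assumption still conflicts with the hypothesis and still does not yield the table. The close agreement also ends at delta 0.10: at the printed numbers with 20% overall, the four rows other than age have about 76% power at 0.15 and 71% at 0.20.

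**Conclusion.** The point holds as a mismatch between a stated assumption and the figures attached to it. The 25% favorable-group rate implies 27.0% to 29.3% overall at delta 0.10, against about 20% under the similarity hypothesis. Table 2 was evidently computed with delta subtracted, so the groups labelled unfavorable carry the lower mortality. Taken at its word, the plan has 69% to 74% power at its delta 0.10 numbers rather than 80%.

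This rests on two-sided 5%, on Table 2's own group shares, and on a continuity correction in the age row only; the correction is inferred from the match. It does not show that 700 is the wrong target. With 20% overall and delta 0.10, 700 falls just short of 80% power for age and clearly short for secondary MDS, and suffices for the other three factors.

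**What to change.** State one expected overall 100-day mortality for the 65+ cohort. For each factor, derive both group rates from that rate and the factor's prevalence, with the unfavorable group higher. State alpha, sidedness and whether a continuity correction is used, apply it alike to all rows, and reissue Table 2. At 20% overall, the totals in the third table above would replace the printed ones. If the sponsor expects a higher overall rate, say so and show the table at that rate.

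Give the resulting power at 700 for delta 0.10, with the assumed unknown share for each factor. At the 500-patient review, examine the pooled observed mortality as well as the factor distribution.

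The cost is one recalculated table and a few sentences; the correction itself requires no extra patients. The downside is that some stated figures become less favourable, chiefly the totals at delta 0.15 and 0.20, and power below 80% for age and secondary MDS at 700 would be stated openly.
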